Appendix C. Patient-reported Outcome Forms/Instruments

C1. SF-36 Version 2

The scoring of SF-36v2 will be processed by QualityMetric's PRO CoRE Software.C2. Scoring algorithm for PROMIS Fatigue SF 7A.

PROMIS SF v1.0 – Fatigue 7A will be scored according to the PROMIS Fatigue Brief Guide including the scoring in the Instrument Section downloaded from

http://www.healthmeasures.net/images/PROMIS/manuals/PROMIS_Fatigue_Scoring_Manual.pdf on 28 Feb 2019.

To calculate the score for PROMIS Fatigue SF 7A, sum the values of the responses to each of the 7 questions. The lowest and highest possible sum is 7 and 35, respectively. Then, use the table below to rescale the score into a standardize score with a mean of 50 and a standard deviation of 10.

Conversion Table	
Raw score	T-score
7	29.4
8	33.4
9	36.9
10	39.6
11	41.9
12	43.9
13	45.8
14	47.6

15	49.2
16	50.8
17	52.2
18	53.7
19	55.1
20	56.4
21	57.8
22	59.2
23	60.6
24	62.0
25	63.4
26	64.8
27	66.3
28	67.8
29	69.4
30	71.1
31	72.9
32	74.8
33	77.1
34	79.8
35	83.2

C3. Scoring algorithm for Modified LupusQoL

The Lupus QoL will be scored using the scoring algorithm from the RWS Life Science website accessed 10 April 2020. <http://www.corptransinc.com/sites/lupusqol/instrument-information/instrument-scoring>

To compute the LupusQOL raw domain score, sum the values of the responses to each question by domain based on the tables below and divide by the number of items. Then, transform the raw domain score by dividing by 4 and multiplying by 100.

Item Response	All the time	Most of the time	A good bit of the time	Occasionally	Never	Not applicable
Score	0	1	2	3	4	Do not score

Domain	Number of Items	Item Numbers
Physical Health	8	1-8
Pain	3	9-11
Planning	3	12-14
Intimate Relationship	2	15, 16
Burden to Others	3	17-19
Emotional Health	6	20-25
Body Image	5	36-30
Fatigue	4	31-34

C4. Scoring algorithm for Patient Global Assessment

The Patient Global Assessment (PtGA) is a 10 cm numeric rating scale with 0 being very well and 10 very poor.

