
 Evaluate the efficacy of rozibafusp alfa on disease flares 	
 Annualized moderate and severe flare rate (as measured by SELENA-SLEDAI Flare Index) over 52 weeks Annualized severe flare rate (as measured by SELENA-SLEDAI Flare Index) over 52 weeks Annualized flare rate (as measured by BILAG score designation of "worse" or "new" resulting in a B score in \geq 2 organs or an A score in \geq 1 organ) over 52 weeks

 Evaluate the efficacy of rozibafusp alfa on joints and skin 	
 Total tender and swollen joints count (limited to hands and wrists): \geq 50% improvement from baseline at week 12, 24, 36, and 52 in subjects with \geq 6 tender and swollen joints involving hands and wrists at baseline Cutaneous Lupus Erythematosus Area and Severity Index (CLASI) activity score \geq 50% improvement from baseline at week 12, 24, 36, and 52 in subjects with a CLASI activity score \geq 8 at baseline

 Describe the efficacy of rozibafusp alfa using patient reported outcomes (PRO) 	
 Patient-Reported Outcome Measurement Information System Fatigue Short Form 7a Instrument (PROMIS-Fatigue SF7A) score and change from baseline at week 12, 24, 36, 44, and 52 Medical Outcomes Short Form 36 version 2 Questionnaire (SF36v2) change from baseline in the physical component score, mental component score and individual domains of SF36v2 at week 12, 24, 36, 44, and 52

Objectives	Endpoints
	
 • Lupus Quality of Life questionnaire (LupusQoL) score and change from baseline at week 12, 24, 36, 44, and 52 • Patient Global Assessment (PtGA) score and change from baseline at week 12, 24, 36, 44, and 52

 • Characterize the safety of rozibafusp alfa 	
 • Treatment-emergent adverse events • Serious adverse events • Clinically significant changes in laboratory values and vital signs

 • Characterize the pharmacokinetics (PK) of rozibafusp alfa 	
 • Trough serum concentrations and terminal elimination half-life of rozibafusp alfa

Objectives	Endpoints
Exploratory	

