8.3 Handling of Missing and Incomplete Data

Subjects may have missing specific data points for a variety of reasons. In general, data may be missing due to a subject's early withdrawal from study, a missed visit, or non-evaluability of a specific clinical or laboratory measurement at its planned clinical visit.

Additionally, as the study was terminated before the planned completion, subjects may have missed clinical visits including not completing the week 52 visit. For efficacy and PRO outcomes, subjects who terminated early due to sponsor decision will be excluded from analyses of data from visits for which they did not have the opportunity to participate in by the date of study termination decision being communicated to sites, i.e. February 28, 2023. Efficacy data collected after this date will be censored and excluded from analyses for that particular visit.

Unless specified, no imputation will be used. The general procedures outlined below describe what will be done when a data point is missing.

Hybrid SLEDAI

In case of completely missing hSLEDAI assessment (e.g. missed visit) or partially missing (e.g. laboratory measurements not available), the missing post-baseline hSLEDAI items will be imputed using last observation carried forward (LOCF) if the previous analysis visit is not missing. Baseline hSLEDAI will not be carried forward to post-baseline.

The hSLEDAI total score will then be computed based on the non-missing and imputed data. **If the hSLEDAI total score cannot be evaluated after imputation, the hSLEDAI score \geq 4 points reduction from baseline will be considered not met.**

CLASI

In case of completely missing CLASI assessment (e.g. missed visit) or partially missing, the missing post-baseline CLASI items will be imputed using LOCF if the previous analysis visit is not missing. Baseline CLASI will not be carried forward to post-baseline.

The CLASI activity score will then be computed based on the non-missing and imputed data. If the CLASI activity score cannot be evaluated after imputation, the CLASI activity score \geq 50% improvement endpoint will be considered not met.

BILAG

In case of completely missing BILAG assessment (e.g. missed visit), the missing post baseline BILAG item scores will be imputed using LOCF if the previous analysis visit is not missing.

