Appendix D. Analytical Windows

The last measurement for the endpoint of interest taken prior to or on the first dose of IP in this study, unless stated otherwise, will be defined as a baseline visit and the analysis visit name will be 'Baseline'. For any visit up to Day 1 pre-dose which is not a baseline visit, the analysis visit will be 'Pre-analysis'.

Since the actual visit for a subject may not exactly coincide with their scheduled visit date, to allow for variations in scheduling, the following visit windows will be used to assign evaluations to a most appropriate nominal visit for analysis and summarization. Furthermore, there will be no gaps between visit windows in order to include as many data points as possible for summarization.

If more than one actual visit (including the unscheduled visits) falls within the same defined window, the visit closest to the target day with non-missing data will be considered for analysis. If two actual visit dates are at the same distance from the target day, the latest visit with non-missing data will be considered for analysis.

The rules above for selecting a visit from multiple ones within the same visit window are not applicable to retest values of lab data. If the lab measurement is a retest, the retest value will be used.

Efficacy assessment (tender/swollen joint count, hSLEDAI, BILAG, SELENA-

SLEDAI Flare Index, PGA, CLASI), weight, and laboratory assessment [REDACTED]

[REDACTED], chemistry, urinalysis)

Study Visit	Target Day	Study Day
Baseline	1	Last evaluation prior to or on Study Day 1
Week 4	29	2 - 42
Week 8	57	43 - 70
Week 12	85	71 - 98
Week 16	113	99 - 126
Week 20	141	127 - 154
Week 24	169	155 - 182
Week 28	197	183 - 210
Week 32	225	211 - 238
Week 36	253	239 - 266
Week 40	281	267 - 294
Week 44	309	295 - 322
Week 48	337	323 - 350
Week 52	365	351 - 394

Hematology

Study Visit	Target Day	Study Day
Baseline	1	Last evaluation prior to or on Study Day 1
Week 4	29	2 - 42
Week 8	57	43 - 70
Week 12	85	71 - 98
Week 16	113	99 - 126
Week 20	141	127 - 154

Week 24	169	155 - 182
Week 28	197	183 - 210
Week 32	225	211 - 238
Week 36	253	239 - 266
Week 40	281	267 - 294
Week 44	309	295 - 322
Week 48	337	323 - 350
Week 52	365	351 - 392
Week 60	421	393 - 448
Week 68	477	≥ 449

Vital sign

Study Visit	Target Day	Study Day
Baseline	1	Last evaluation prior to or on Study Day 1
Week 2	15	2 - 21
Week 4	29	22 - 35
Week 6	43	36 - 49
Week 8	57	50 - 63
Week 10	71	64 - 77
Week 12	85	78 - 91
Week 14	99	92 - 105

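### SAP Appendix D splits PRO weeks 12 and 24 at day 99 instead of the midpoint, day 127; separately, the LupusQoL formula read literally gives a 'Not applicable' item the value 0

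*SAP*

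**What the plan says.** **Endpoints.** SAP Section 2.1 lists as a secondary endpoint "Lupus Quality of Life questionnaire (LupusQoL) score and change from baseline at week 12, 24, 36, 44, and 52". The SF-36v2, PROMIS Fatigue and Patient Global Assessment are reported at the same weeks. Table 9-2 summarises all four descriptively by randomized arm.

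**Windows.** SAP Appendix D says that "the following visit windows will be used to assign evaluations to a most appropriate nominal visit for analysis and summarization". The PRO table gives:

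| Visit | Target day | Window (study days) |
|---|---|---|
| Week 4 | 29 | 2–56 |
| Week 12 | 85 | 57–98 |
| Week 24 | 169 | 99–210 |
| Week 36 | 253 | 211–280 |
| Week 44 | 309 | 281–336 |
| Week 52 | 365 | 337–394 |

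Where several records fall in one window, "the visit closest to the target day with non-missing data will be considered for analysis"; a tie goes to the later record.

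**LupusQoL scoring.** Appendix C3 opens with "The Lupus QoL will be scored using the scoring algorithm from the RWS Life Science website accessed 10 April 2020". It then writes out a formula: "sum the values of the responses to each question by domain based on the tables below and divide by the number of items", followed by "transform the raw domain score by dividing by 4 and multiplying by 100". Responses run from 0 (All the time) to 4 (Never), and 'Not applicable' is marked as not to be scored. The domain table has a column of fixed item counts: 8, 3, 3, 2, 3, 6, 5 and 4. Body Image is given as items 36-30.

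**Missing data.** Section 8.3 has no rule for LupusQoL items. Its default is "Unless specified, no imputation will be used".

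**The concern.** The day 98/99 cut belongs between weeks 12 and 16, and it is used correctly there in the efficacy, hematology and pharmacokinetic tables. The PRO table has no week 16 or week 20, so the same cut leaves a block of days attached to the farther visit. That conflicts with the stated aim of assigning each record to the most appropriate visit. A late week 12 questionnaire would drop out of the week 12 summary and could appear as a week 24 result.

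In Appendix C3, the denominator phrase "number of items" matches the heading of the column of fixed counts. Nothing says that the denominator shrinks when an item is not applicable, or when a domain becomes missing. A programmer who follows the text can compute a domain score that treats an irrelevant question as the lowest scored answer. A subject whose 'Not applicable' answers differ between visits would then show a change that no answered item supports.

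**Working it through.** **1. PRO boundaries**

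Inputs are the target days and windows above. The rule tested is that the later window starts at the midpoint of two adjacent targets, with a tie going to the later visit.

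| Boundary | Midpoint of targets | SAP start of later window |
|---|---|---|
| Week 4 / 12 | (29 + 85)/2 = 57 | 57 |
| Week 12 / 24 | (85 + 169)/2 = 127 | **99** |
| Week 24 / 36 | (169 + 253)/2 = 211 | 211 |
| Week 36 / 44 | (253 + 309)/2 = 281 | 281 |
| Week 44 / 52 | (309 + 365)/2 = 337 | 337 |

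The rule reproduces four of the five PRO boundaries. Over all the Appendix D tables it reproduces 72 of 73, and this is the only exception. The source of the day-99 cut is visible in the tables that have a week 16 (target day 113): (85 + 113)/2 = 99.

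The misassigned block is days 99–126, which is 126 − 99 + 1 = 28 days. At its ends:

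- Day 99 is 99 − 85 = 14 days from week 12 and 169 − 99 = 70 days from week 24.
- Day 126 is 126 − 85 = 41 days from week 12 and 169 − 126 = 43 days from week 24.

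**2. When the block changes a result**

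- *Week 12.* A record on days 99–126 cannot supply the week 12 value. If the subject has nothing on days 57–98, week 12 is missing, because no imputation is specified for these outcomes.
- *Week 24.* Records on days 99–126 are 43 to 70 days from day 169. Records on days 127–210 are at most 169 − 127 = 42 days away. Any record on days 127–210 is therefore chosen first, and a misassigned record is used only when there is none.
- *On-schedule visits.* Protocol Section 9.1.2 allows 3 business days either side. With one weekend that is 5 calendar days, so a week 12 visit falls by about day 85 + 5 = 90, well short of day 99.

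**3. LupusQoL**

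With n items in the domain, the literal score is (sum of scored items / n) / 4 × 100. With one 'Not applicable' item, only n − 1 items add to the sum. The literal score is then (n − 1)/n times the score based on answered items only, and it equals the score had the item been answered 'All the time' (0).

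One 'Not applicable', all other items 'Never' (answered-items score 100 throughout):

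| Domain | n | Literal score | Shortfall |
|---|---|---|---|
| Physical Health | 8 | 87.5 | 12.5 |
| Emotional Health | 6 | 83.3 | 16.7 |
| Body Image | 5 | 80 | 20 |
| Fatigue | 4 | 75 | 25 |
| Pain, Planning, Burden to Others | 3 | 66.7 | 33.3 |
| Intimate Relationship | 2 | 50 | 50 |

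For Intimate Relationship: (4/2)/4 × 100 = 50, against (4/1)/4 × 100 = 100.

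For a change score, suppose a subject gives one 'Not applicable' and one 'Occasionally' (3) at baseline, then 'Occasionally' to both later. The literal scores are (3/2)/4 × 100 = 37.5 and (6/2)/4 × 100 = 75. That is an apparent gain of 37.5, although the item answered at both visits did not change.

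**4. Body Image items**

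The counts sum to 8 + 3 + 3 + 2 + 3 + 6 + 5 + 4 = 34. The neighbouring domains use items 20-25 and 31-34, so the five Body Image items can only be 26-30.

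**The case against.** *On the window.* The SAP never states a midpoint rule, and the practical reach is small: on-schedule visits are untouched, and any record on days 127–210 displaces a misassigned one. A reader might infer that early termination of the trial moved many early PROs into week 24. The documents do not support that. Section 8.3 excludes subjects stopped by the sponsor's decision from visits they had no opportunity to attend by 28 February 2023. What remains is late records, unscheduled records and early terminations for other reasons. The departure still stands, because the midpoint pattern holds at all 72 other boundaries.

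*On LupusQoL.* C3 defers to a website algorithm that is not in the documents and may settle the matter. The table marks 'Not applicable' as unscored instead of assigning 0, so dropping the item from the denominator is a natural reading. Counting it as 0 would in effect be an imputation, and none is specified. If every item in a domain is 'Not applicable' there is nothing to sum, and missing is the natural result. A reader might infer that LupusQoL domain means are biased downward by some definite number of points. The documents do not support that either: it requires the literal reading to be the one programmed, and a frequency of 'Not applicable' that is nowhere given. What stands is that the written formula and the fixed-count column lead to the literal reading, and neither C3 nor Section 8.3 rules it out.

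*On stakes.* SAP Section 10 removed the treatment comparisons. No test, error rate or power figure depends on either point.

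**Conclusion.** The PRO window boundary is an error in the SAP. Days 99–126, 28 days in all, are assigned to the farther visit for all four PROs. The effect is confined to late, unscheduled or non-sponsor early-termination records. Their number is not in the documents, so the effect on arm summaries cannot be computed. This conclusion takes the midpoint rule from the pattern of the other boundaries.

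The LupusQoL point is an underspecified rule with a harmful literal reading. Under that reading, one 'Not applicable' costs up to 12.5 points in the longest domain and up to 50 in the shortest. Whether any bias arises, and its size, depends on the cited algorithm, the programming and the frequency of 'Not applicable'. That 0 is the least favourable answer is inferred from the response table, since item wording is not given.

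The Body Image range is a clerical slip. All three merit correction, and none bears on the primary endpoint.

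**What to change.** - **Appendix D, PRO table:** set week 12 to days 57–126 and week 24 to days 127–210. Day 127 is a tie and goes to the later visit, as at the other boundaries.
- **Appendix C3, formula:** divide by the number of items actually scored. Set the domain to missing when no item is scored, or when the minimum required by the cited instrument algorithm is not met, and write that minimum into the SAP. The half-evaluable rule for joint counts in Section 8.3 should not simply be borrowed, since it might conflict with that algorithm.
- **Appendix C3, Body Image:** change 36-30 to 26-30.

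The cost is a few appendix edits and minor reprogramming. Some LupusQoL domain scores may become missing where the literal formula would have returned a number, so the count of subjects with a score should be shown for each domain and visit.

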Appendix D. Analytical Windows

The last measurement for the endpoint of interest taken prior to or on the first dose of IP in this study, unless stated otherwise, will be defined as a baseline visit and the analysis visit name will be 'Baseline'. For any visit up to Day 1 pre-dose which is not a baseline visit, the analysis visit will be 'Pre-analysis'.

Since the actual visit for a subject may not exactly coincide with their scheduled visit date, to allow for variations in scheduling, the following visit windows will be used to assign evaluations to a most appropriate nominal visit for analysis and summarization. Furthermore, there will be no gaps between visit windows in order to include as many data points as possible for summarization.

If more than one actual visit (including the unscheduled visits) falls within the same defined window, the visit closest to the target day with non-missing data will be considered for analysis. If two actual visit dates are at the same distance from the target day, the latest visit with non-missing data will be considered for analysis.

The rules above for selecting a visit from multiple ones within the same visit window are not applicable to retest values of lab data. If the lab measurement is a retest, the retest value will be used.

Efficacy assessment (tender/swollen joint count, hSLEDAI, BILAG, SELENA-

SLEDAI Flare Index, PGA, CLASI), weight, and laboratory assessment [REDACTED]

[REDACTED], chemistry, urinalysis)

Study Visit	Target Day	Study Day
Baseline	1	Last evaluation prior to or on Study Day 1
Week 4	29	2 - 42
Week 8	57	43 - 70
Week 12	85	71 - 98
Week 16	113	99 - 126
Week 20	141	127 - 154
Week 24	169	155 - 182
Week 28	197	183 - 210
Week 32	225	211 - 238
Week 36	253	239 - 266
Week 40	281	267 - 294
Week 44	309	295 - 322
Week 48	337	323 - 350
Week 52	365	351 - 394

Hematology

Study Visit	Target Day	Study Day
Baseline	1	Last evaluation prior to or on Study Day 1
Week 4	29	2 - 42
Week 8	57	43 - 70
Week 12	85	71 - 98
Week 16	113	99 - 126
Week 20	141	127 - 154

Week 24	169	155 - 182
Week 28	197	183 - 210
Week 32	225	211 - 238
Week 36	253	239 - 266
Week 40	281	267 - 294
Week 44	309	295 - 322
Week 48	337	323 - 350
Week 52	365	351 - 392
Week 60	421	393 - 448
Week 68	477	≥ 449

Vital sign

Study Visit	Target Day	Study Day
Baseline	1	Last evaluation prior to or on Study Day 1
Week 2	15	2 - 21
Week 4	29	22 - 35
Week 6	43	36 - 49
Week 8	57	50 - 63
Week 10	71	64 - 77
Week 12	85	78 - 91
Week 14	99	92 - 105
Week 16	113	106 - 119
Week 18	127	120 - 133
Week 20	141	134 - 147
Week 22	155	148 - 161
Week 24	169	162 - 175

Week 26	183	176 - 189
Week 28	197	190 - 203
Week 30	211	204 - 217
Week 32	225	218 - 231
Week 34	239	232 - 245
Week 36	253	246 - 259
Week 38	267	260 - 273
Week 40	281	274 - 287
Week 42	295	288 - 301
Week 44	309	302 - 315
Week 46	323	316 - 329
Week 48	337	330 - 343
Week 50	351	344 - 357
Week 52	365	358 - 378
Week 56	393	379 - 406
Week 60	421	407 - 434
Week 64	449	435 - 462
Week 68	477	≥ 463

, SDI

Study Visit	Target Day	Study Day
Baseline	1	Last evaluation prior to or on Study Day 1
Week 24	169	2 - 266
Week 52	365	267 - 394

Pharmacokinetic assessment

Study Visit	Target Day	Study Day
Baseline	1	Last evaluation prior to or on Study Day 1
Week 4	29	2 - 42
Week 8	57	43 - 70
Week 12	85	71 - 98
Week 16	113	99 - 126
Week 20	141	127 - 154
Week 24	169	155 - 210
Week 36	253	211 - 280
Week 44	309	281 - 336
Week 52	365	337 - 378
Week 56	393	379 - 406
Week 60	421	407 - 434
Week 64	449	435 - 462
Week 68	477	≥ 463

PROs (SF-36v2, PROMIS Fatigue SF 7A, LupusQOL, PtGA)

Study Visit	Target Day	Study Day
Baseline	1	Last evaluation prior to or on Study Day 1
Week 4	29	2 - 56
Week 12	85	57 - 98
Week 24	169	99 - 210
Week 36	253	211 - 280
Week 44	309	281 - 336
Week 52	365	337 - 394

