- The appropriate case report form (CRF) (eg, Event CRF) that captures information necessary to facilitate the evaluation of treatment-emergent liver abnormalities is to be completed and sent to Amgen

Other events of hepatotoxicity and potential DILI are to be reported as serious adverse events if they meet the criteria for a serious adverse event defined in Section 12.4.

Additional Clinical Assessments and Observation

All subjects in whom investigational product(s) or protocol-required therapies is/are withheld (either permanently or conditionally) due to potential DILI as specified in [Table 12-2](#) OR who experience AST or ALT elevations $> 3 \times$ upper limit of normal (ULN) or 2-fold increases above baseline values for subjects with elevated values before drug are to undergo a period of “close observation” until abnormalities return to normal or to the subject’s baseline levels. **Tests may be performed locally as required per investigator discretion.**

Assessments that are to be performed during this period include:

- Repeat AST, ALT, ALP, bilirubin (BIL) (total and direct), and INR within 24 hours
- In cases of TBL $> 2 \times$ ULN or INR > 1.5 , retesting of liver tests, BIL (total and direct), and INR is to be performed every 24 hours until laboratory abnormalities improve

Testing frequency of the above laboratory tests may decrease if the abnormalities stabilize or the investigational product(s) or protocol-required therapies has/have been discontinued AND the subject is asymptomatic.

Initiate investigation of alternative causes for elevated AST or ALT and/or elevated TBL.

The following are to be considered depending on the clinical situation:

- Complete blood count with differential to assess for eosinophilia
- Serum total immunoglobulin (Ig)G, antinuclear antibody anti-smooth muscle antibody, and liver kidney microsomal antibody-1 to assess for autoimmune hepatitis
- Serum acetaminophen (paracetamol) levels
- A more detailed history of:
 - Prior and/or concurrent diseases or illness
 - Exposure to environmental and/or industrial chemical agents
 - Symptoms (if applicable) including right upper quadrant pain, hypersensitivity-type reactions, fatigue, nausea, vomiting and fever
 - Prior and/or concurrent use of alcohol, recreational drugs and special diets

- Concomitant use of medications (including non-prescription medicines and herbal and dietary supplements), plants, and mushrooms
- Viral serologies

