9.6.2 Laboratory Test Results

Selected clinical laboratory test results, change and percent change from baseline will be summarized over time by treatment arm. In addition, shift tables from baseline to the worst on-study laboratory toxicity based on the CTCAE version 5, will be presented.

Table 9-4 Selected Safety Laboratory Tests

Chemistry	Hematology	Urinalysis
Creatinine	RBC	Protein/creatinine ratio
Total bilirubin	Hemoglobin	WBC
AST (SGOT)	Hematocrit	RBC
ALT (SGPT)	MCV	
C-reactive Protein	Reticulocytes	Platelets
	WBC	
	Differential	
	
 • Eosinophils • Basophils • Lymphocytes 	

ALT = alanine aminotransferase; AST = aspartate aminotransferase; MCV = mean corpuscular volume; RBC = red blood cell count; SGOT = serum glutamic-oxaloacetic transaminase; SGPT = serum glutamic-pyruvic transaminase; WBC = white blood cell count

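### SAP Appendix D uses a laboratory retest in place of the original without limit, and the protocol's liver repeats follow abnormal values, so by-visit ALT, AST and bilirubin summaries can be pulled towards later, often recovering, values

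*SAP*

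**What the plan says.** SAP Appendix D sets up visit windows "to assign evaluations to a most appropriate nominal visit for analysis and summarization". When several visits, including unscheduled ones, fall in one window, "the visit closest to the target day with non-missing data will be considered for analysis", and a tie goes to the later visit. That choice depends on dates only.

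Laboratory data then get an exception: "The rules above for selecting a visit from multiple ones within the same visit window are not applicable to retest values of lab data". The instruction that follows is "If the lab measurement is a retest, the retest value will be used".

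SAP Section 9.6.2 names two laboratory outputs:
- By-visit summaries: "Selected clinical laboratory test results, change and percent change from baseline will be summarized over time by treatment arm". Table 9-4 includes ALT, AST and total bilirubin.
- Peak toxicity: "shift tables from baseline to the worst on-study laboratory toxicity based on the CTCAE version 5, will be presented". Protocol Section 10.3.2.3.3 has the same worst on-study basis.

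Protocol Section 12.7 (Appendix 7) contains the repeat-testing orders:
- AST, ALT, ALP, bilirubin and INR are repeated within 24 hours when AST or ALT exceeds 3x ULN, when it doubles from an elevated baseline, or when product is withheld for potential drug-induced liver injury.
- Only when total bilirubin exceeds 2x ULN or INR exceeds 1.5 does the text add that "retesting of liver tests, BIL (total and direct), and INR is to be performed every 24 hours until laboratory abnormalities improve".
- Follow-up continues until values return to normal or baseline, or are judged stable.

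The other retest provision found is in Protocol Section 9.1.1. It concerns screening and needs sponsor approval.

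**The concern.** A rule for choosing between duplicate records should not depend on the results. Closest-to-target meets that standard once two records exist. The retest exception does not, where the second sample was drawn because the first was abnormal: the original is set aside because it was high, and no order was found to repeat normal values that would offset this. Where testing continues until values improve, the last retest is an improved one by construction.

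Clinically significant change in laboratory values is a stated safety endpoint. If abnormal liver values at a visit are represented by later ones, mean values and mean changes at that visit can understate the excursion, and more so in an arm with more liver abnormalities.

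**Working it through.** The plan gives no figure for this rule, so there is none to reproduce. Two checks show what the wording does.

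**Check A: how often the retest rule changes the by-visit record**

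Inputs:
- The closest-to-target rule with ties to the later visit (SAP Appendix D).
- Visits within 3 business days of schedule (Protocol Section 9.1.2), treated here as 3 calendar days.
- Retest lags of 1, 2, 3 and 7 days, and equal weight for each visit day, both assumed.

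Let d be the day of the original minus the target day, from -3 to +3, and L the lag. The default rule picks the retest when |d + L| <= |d|, that is, when d <= -L/2.

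| L (days) | d at which the default already picks the retest | Default keeps the original |
|---|---|---|
| 1 | -3, -2, -1 | 4 of 7 (57%) |
| 2 | -3, -2, -1 (tie at -1) | 4 of 7 (57%) |
| 3 | -3, -2 | 5 of 7 (71%) |
| 7 | none | 7 of 7 (100%) |

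The last column is the share of visit days on which the retest rule changes the selected record. The latest retest considered falls on day +10 (3 + 7). The chemistry windows from Week 8 to Week 48 run to 13 days after target (Week 8: target day 57, window to day 70), so original and retest share a window in every case.

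**Check B: what would happen if the worst grade were also taken from the retest only**

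Inputs:
- The cut-offs of 3x, 5x and 8x ULN for AST/ALT in Protocol Table 12-2, used only as a yardstick. They are not CTCAE grades.
- Assumed original ALT values of 3.5, 5.5, 8.5 and 12x ULN.
- Assumed retest changes of +20%, 0, -10%, -20%, -30% and -50%.

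A value x no longer exceeds its highest cut-off T once the retest falls by at least 1 - T/x:
- 3.5x: 1 - 3/3.5 = 14.3%; lost in 3 of 6 cases
- 5.5x: 1 - 5/5.5 = 9.1%; lost in 4 of 6
- 8.5x: 1 - 8/8.5 = 5.9%; lost in 4 of 6
- 12x: 1 - 8/12 = 33.3%; lost in 1 of 6

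With only the retest kept, the highest cut-off is lost in 3 + 4 + 4 + 1 = 12 of 24 cases, and in none of the 8 where the retest is equal or higher. With all records kept, it is lost in 0 of 24. These counts illustrate the mechanism and do not estimate a rate, because the documents give no distribution of retest values.

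**Which output each rule reaches**

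The by-visit summaries need one record per window, so the Appendix D exception applies to them directly. The shift tables are described by a study-wide worst value, which does not need a window. The SAP neither says that the worst value runs over all records nor that it is limited to window-selected ones.

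**The case against.** The strongest case against is that the rule is written for visit selection, while toxicity is reported as worst on-study. A reader might infer that Appendix D removes the peaks that define toxicity from the shift tables. The documents do not support that. A worst on-study value is by name a maximum, and SAP Section 8.3 leans the conservative way by assigning the worse grade when grading information is missing or ambiguous. What stands is that no sentence fixes which records enter the maximum.

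A reader might also infer that an isolated high ALT is retested daily until it recovers. The protocol's daily order applies only with raised bilirubin or INR. For ALT or AST alone, the 24-hour order is one repeat, which may be higher, equal or lower. Nor do the documents support extending the point to other analytes: the standing abnormality-driven order found covers liver tests only. Of those tests, ALP and INR are not in Table 9-4.

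It is also open whether close-observation samples are retests or unscheduled visits, which the default rule covers. Section 12.7 does use the word retesting for the bilirubin/INR series, so the first reading is available, but it is not the only one.

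Finally, liver injury is recorded elsewhere. Concurrent AST/ALT and bilirubin/INR elevation must be reported as a serious adverse event, and potential liver-injury data go on the CRF. This limits the harm but is not a full substitute. Other hepatotoxicity is reported as serious only if it meets the usual criteria, and Protocol Section 9.2.4 leaves abnormalities judged not clinically significant generally unrecorded as adverse events.

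**Conclusion.** The concern holds for the by-visit summaries. To the extent that protocol-ordered liver repeats are treated as retests, the stated rule makes record selection for ALT, AST and bilirubin depend on the result, and it can move abnormal visits towards later, often recovering, values. Compared with the default rule it changes the record on 57% to 100% of visit days, given equal weighting, visits within 3 calendar days of target and lags of 1 to 7 days. The effect on arm means cannot be sized, because neither the number of subjects retested nor their values are given.

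For the shift tables, loss of peaks is possible and not demonstrated. It would require the worst grade to be derived from window-selected records, which the SAP neither states nor excludes.

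Safety is summarised descriptively and the SAP removes treatment comparisons, so no formal test is affected. Severity is low to moderate.

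**What to change.** In SAP Appendix D, limit the retest rule to originals that the laboratory reports as invalid, and to screening retests. Apply the closest-to-target rule to all other valid post-baseline laboratory results, including liver repeats. This makes the choice between two valid records depend on timing only. It does not keep the original every time: under Check A, a one-day repeat would still be selected on 3 of 7 visit days.

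In SAP Section 9.6.2, state that worst on-study toxicity is taken over all valid post-baseline results: originals, retests and unscheduled samples.

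The cost is two sentences of SAP text and minor reprogramming, with no new data. By-visit liver values may look slightly less favourable.
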